11. MEASUREMENT OF EFFECT

11.1. Antitumor Effect

11.1.1. Imaging Modalities

At baseline and follow-up, systemic response (for unirradiated lesions) and local response (for irradiated lesions) will be assessed using FDG-PET/CT (preferred) or CT scan of the chest/abdomen/pelvis. Ideally IV contrast and CT slice thickness $\leq 5\text{mm}$ will be used for either type of study. Images will be acquired according to the standard of care schedule used for patients receiving immune checkpoint therapy, at intervals of 4 months or less after initiation of immune therapy. In the event of an imaging study showing disease progression, a confirmatory scan is recommended at least 4 weeks later to confirm progression. The same method of assessment and technique should be used to characterize each index lesion at baseline and during follow-up. All measurements should be recorded in metric notation and specified to the nearest millimeter. All baseline evaluations should be performed as closely as possible to the beginning of treatment and never more than 4 weeks before the beginning of the treatment. Imaging-based evaluation is preferred to evaluation by clinical examination unless the lesion(s) being followed cannot be imaged but are assessable by clinical exam.

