3.3. Expected Duration of Treatment and Subject Participation

Each course of radiation therapy will be 3-5 fractions delivered over 3-21 days. The first course of radiation will be initiated at any time point between the date of cycle 1 of immune therapy through the date of cycle 2 of immune therapy. The duration of immune therapy administration and the number of courses of radiation therapy that a subject receives will be dependent upon the subject's response to prior treatment. There is no specific maximum number of cycles of immune therapy if a patient continues to respond to treatment, or courses of radiation therapy if a patient has persistent stable disease on imaging. Progressive disease will be defined per irRC criteria as assessed by two imaging studies \geq 4 weeks apart. Because abscopal responses have been reported even when the radiation is given after the immune therapy was completed, a final course of radiation therapy will be offered to patients at the time of progressive disease on imaging.³⁸⁻³⁹ Subsequent therapy decisions will be at the discretion of the treating physicians, including the option of continuing the immune therapy past progression if clinically indicated.

The radiation therapy or immune therapy may be cancelled or discontinued at any point if no longer medically advisable due to intercurrent illness, toxicity/adverse event, decline in performance status, pregnancy, the best interests of the patient, or death. Subjects may also withdraw consent from treatment (partial consent) or from the study (full consent).

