11.2. Response Criteria

The irRC criteria for assessing systemic disease response (including only non-irradiated lesions) can be seen in the following table:

New, measurable lesions (ie, $\geq 5 \times 5$ mm)	Incorporated into tumor burden
New, non-measurable lesions (ie, $< 5 \times 5$ mm)	Do not define progression (but preclude irCR)
Non-index lesions	Contribute to defining irCR (complete disappearance required)
irCR	Disappearance of all lesions in two consecutive observations at least 4 weeks apart
irPR	$\geq 50\%$ decrease in tumor burden compared with baseline in two observations at least 4 weeks apart
irSD	Neither sufficient decrease in tumor burden to qualify as irPR

	nor sufficient increase in tumor burden to qualify as irPD.
irPD	$\geq 25\%$ increase in tumor burden compared with nadir (at any single time point) in two consecutive observations at least 4 weeks apart.

Examples of irRC overall response³⁷:

Measurable response Index and new, measurable lesions (tumor burden),* %	Nonmeasurable response		Overall response Using irRC
	Non-index lesions	New, nonmeasurable lesions	
↓100	Absent	Absent	irCR [†]
↓100	Stable	Any	irPR [†]
↓100	Unequivocal progression	Any	irPR [†]
↓≥50	Absent/Stable	Any	irPR [†]
↓≥50	Unequivocal progression	Any	irPR [†]
↓<50 to <25↓	Absent/Stable	Any	irSD
↓<50 to <25↓	Unequivocal progression	Any	irSD
≥25↓	Any	Any	irPD [†]

*Decreases assessed relative to baseline, including measurable lesions only (>5 x 5 mm).
†Assuming response (irCR) and progression (irPD) are confirmed by a second, consecutive assessment at least 4 wk apart.

RECIST version 1.1 will be used to assess the local response of irradiated lesions only, taking as reference the baseline largest diameter:

Complete Response (CR)	Disappearance of the irradiated lesion
Partial Response (PR)	$\geq 30\%$ decrease in the single largest diameter of the irradiated lesion
Stable Disease (SD)	Neither sufficient decrease in diameter to qualify as PR nor sufficient increase in diameter to qualify as PD
Progressive Disease (PD)	$\geq 20\%$ increase in the single largest diameter of the irradiated lesion. In addition to the relative increase of 20%, the sum must also demonstrate an absolute increase of at least 5 mm (0.5 cm).

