11.2.1. Best Overall Response

The best response recorded from the start of the treatment until disease progression/recurrence (taking as reference for progressive disease the smallest measurements recorded since the treatment started). The patient's best response assignment will depend on the achievement of both measurement and confirmation criteria.

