11.2.2. Progression-Free Survival

The duration of time from start of treatment to time of progression or death, whichever occurs first. For those patients with a CR or PR, the reference for progressive disease the smallest measurements recorded since the treatment started).

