13.2. Sample Size/Accrual Rate

The primary analysis will be for patients enrolled at time-points (A) and (B) above, whereas patients enrolled at time-point (C) will be included in observational analysis only (see section 3.1). The primary endpoint of this study is the overall response rate (complete + partial response) and the efficacy will be assessed using the Simon's two-stage Minmax design. A sample size of 33 patients is chosen to differentiate between the response rate of 20% and 40% with 80% power at a significance level of 0.05. In particular, 18 patients will be enrolled at the first stage. If 15 or more of the first 18 patients have disease progression prior to any response, the trial will be terminated; otherwise an additional 15 patients will be treated for a total of 33 patients. In the final data analysis, if 10 or fewer patients respond among 33 patients, the treatment will be concluded ineffective. The probability of early termination due to futility is 0.72.

For correlative study between biomarkers and response, this sample size will have at least 80% power to detect a 50% change/difference on biomarker data between response and non-response groups using a two-sided two-sample t-test at 0.05 significance level, assuming that the response rate is 35% or higher and the coefficient of variation (CV) of biomarkers is 0.45.

Approximately 100 patients with metastatic NSCLC are diagnosed and treated each year at our institution, many of whom will be candidates for immune checkpoint therapy. As such, we expect to accrue 3 patients per month to this trial for an estimated accrual period of one year. The full estimated duration of the study is two years.

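### Progression needs a second scan that the plan only recommends, and no PFS rule covers a patient with one worsening scan who is never rescanned

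*Combined protocol and SAP*

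**What the plan says.** Three places make confirmation part of the definition of progression.

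- Section 3.3: "Progressive disease will be defined per irRC criteria as assessed by two imaging studies" at least 4 weeks apart.
- Section 11.2, irPD row: a 25% or greater "increase in tumor burden compared with nadir (at any single time point) in two consecutive observations at least 4 weeks apart".
- Section 11.2, footnote to the examples: "Assuming response (irCR) and progression (irPD) are confirmed by a second, consecutive assessment at least 4 wk apart".

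Section 11.1.1 does not require the confirming scan. After a scan showing progression, "a confirmatory scan is recommended at least 4 weeks later to confirm progression". The imaging that is required is one scan at least every 4 months (Section 10.2, footnote 16; Section 11.1.1 gives the same interval).

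Stable disease is the residual class. It covers a patient with neither enough decrease for irPR "nor sufficient increase in tumor burden to qualify as irPD".

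PFS is defined in Section 11.2.2 as "The duration of time from start of treatment to time of progression or death, whichever occurs first". Section 13.3 names Kaplan-Meier and gives no event or censoring conventions. Under Section 3.4, follow-up stops 30 days after progression or a new systemic therapy. After that point the calendar in Section 10.2 schedules only a survival check and an optional rebiopsy.

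The stage 1 rule in Section 13.2 is also written in progressions: "If 15 or more of the first 18 patients have disease progression prior to any response, the trial will be terminated".

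**The concern.** The definition needs a second observation that the schedule does not guarantee, and no default applies when it is missing. Consider a patient whose first follow-up scan shows a clear increase and who then starts another drug, withdraws or is too unwell for a further scan. That patient does not meet irPD, falls into the residual stable class, and has no progression date. Clinical progression is not defined, so nothing else in Section 11 fills the gap.

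Missing scans are unlikely to be random. Switching and decline both tend to follow a bad first scan, so the lost events would come from patients doing poorly. One-year PFS is a named secondary objective (Section 1.2), and Section 13.3 plans comparison with earlier trials of checkpoint inhibitors alone where applicable. In a single-arm study, an upward shift caused by event counting could be read as benefit from the radiation.

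**Working it through.** **Which patients are affected.**

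- *Remains on study without a new therapy.* The patient is still in the calendar columns for follow-up before documented progression, and a scan is due within 4 months. If it falls at least 4 weeks after the first and still shows the increase, it confirms irPD. No event is lost.
- *Switches systemic therapy.* The confirming scan cannot come before day 28 after the first, follow-up ends 30 days after the switch, and no imaging is scheduled after the switch. For a switch soon after the first scan there is little room for a second.
- *Withdraws or is too ill to be scanned.* No second scan is obtained.
- *Dies.* Death is a PFS event, but dated later than the scan. Section 3.4 says survival data may be obtained from records or by phone with the patient's agreement, so capture is likely but not assured.

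**Effect on 1-year PFS.** The plan states no PFS figure to reproduce and no rate of missed confirmation, so all inputs are assumptions: exponential times; true 1-year PFS S = 0.25, hence λ = −ln 0.25 = 1.386 per year; every first event is a progression; a share f is unconfirmed; no other censoring before 12 months.

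*(a) Censored at the first progression scan.* The observed hazard is (1 − f)λ, so the estimate is S^(1−f). For f = 0.2: 0.25^0.8 = 0.330.

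*(b) Counted at death.* Let T be the time to progression and D the exponential time from progression to death, with rate μ = ln 2 / median. The estimate is S + f × P(T ≤ 1 < T + D), where the probability is λ/(μ − λ) × (e^−λ − e^−μ), or λe^−λ when μ = λ.

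- Median 3 months: μ = 2.773; probability = 1 × (0.25 − 0.0625) = 0.1875; estimate = 0.25 + 0.2 × 0.1875 = 0.288.
- Median 6 months: μ = 1.386 = λ; probability = 1.386 × 0.25 = 0.347; estimate = 0.25 + 0.2 × 0.347 = 0.319.

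| Share unconfirmed | Death captured, median 3 months | Death captured, median 6 months | Censored at first progression scan |
|---|---|---|---|
| 10% | 27% | 28% | 29% |
| 20% | 29% | 32% | 33% |
| 30% | 31% | 35% | 38% |

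The true value is 25% throughout. The censored column is not a strict ceiling: with a 9-month median and 20% unconfirmed, counting at death gives 34%.

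**Effect on the primary endpoint.** Section 11.2.1 says "The patient's best response assignment will depend on the achievement of both measurement and confirmation criteria". A patient with one worsening scan, no confirmed response and no later scan is a non-responder whether or not progression is confirmed.

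**Stage 1.** An exact search with response rates of 20% and 40%, alpha at most 0.05 and power at least 80% reproduces the plan's minimax design: stop at 4 or fewer responders of 18, conclude ineffective at 10 or fewer of 33, alpha 0.046, power 0.801, early-termination probability 0.716 (stated as 0.72). The written rule of 15 or more progressions of 18 equals 3 or fewer responders if every non-responder progresses. At a 20% response rate it then stops with probability 0.501. If only 90% or 80% of non-responders have confirmed progression, P(Bin(18, 0.8 × 0.9) ≥ 15) = 0.214 and P(Bin(18, 0.8 × 0.8) ≥ 15) = 0.067.

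**The case against.** The strongest reply is that the plan expects rescanning and already counts death. Scans at intervals of 4 months or less are required, Section 5.3 calls for reimaging after each further course of radiation, and footnote 18 in Section 10.2 refers to a confirmatory study showing progression. A reader might infer that anyone not sent for the extra early scan drops out of the progression count. The documents do not support that, because a later required scan can confirm. This part of the reply stands and limits the problem to patients who switch, withdraw or cannot be scanned.

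A reader might also infer that the plan classes such patients as censored. It does not; Sections 11.2.2 and 13.3 are silent. Because death counts, the sickest patients tend to give late events rather than lost ones. That also stands. At 20% unconfirmed it brings the inflation down from about 8 points to about 4 to 7, but does not remove it.

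Third, irRC asks for confirmation for a reason: Section 11.1.2 notes that disease may worsen transiently before it stabilises or regresses. That supports letting a later scan overturn a first one. It does not supply a rule for when no later scan exists.

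Finally, a reader might blame missing confirmation for a weak futility stop. It does lower the stopping probability under the literal rule. However, that rule gives 0.50 rather than 0.72 even with full confirmation, so its main fault is the count and cut-off. Even if stage 1 never stopped the trial, 11 or more responders of 33 has type I error 0.051, against 0.046 as designed.

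**Conclusion.** The concern holds for a defined subgroup: patients with one qualifying scan and no later one because they switched therapy, withdrew or became too ill. As written they never meet progression, and they enter PFS only through a recorded death. The direction of bias in 1-year PFS is likely upward. With a true value of 25% and 20% unconfirmed, the estimate is about 29% to 32% when deaths are captured at 3 to 6 months median, and 33% under censoring at the first progression scan. These sizes rest on assumed exponential times and an assumed share, since the documents give neither. The primary response rate is essentially unaffected. The point is worth correcting before analysis but does not threaten the main conclusion.

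**What to change.** Section 11.2.2: date progression at the first scan with an increase of at least 25% when it is confirmed. Also count it at that scan when no later scan is obtained because of death, clinical deterioration or new systemic therapy. Put loss to follow-up after a single progression scan into a sensitivity analysis that counts every first-scan progression as an event.

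Section 13.2: state the stage 1 rule in confirmed responders, 4 or fewer of 18. This reproduces the stated 0.72 and no longer depends on how progression is confirmed.

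Reconcile Sections 3.3, 11.1.1, 11.2, 11.2.2 and 13.2 so that one definition of progression applies. These are endpoint-counting rules and take no position on treatment decisions.

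The cost is a few sentences and no extra scans. The downside is that an occasional pseudo-progressor without a second scan counts as an event, which makes PFS slightly less favourable.

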11.1.2. Definitions

Evaluable for objective response: Only those patients who have received at least one course of radiation therapy, and have had their disease re-evaluated by imaging at least 4 weeks after initiation of therapy will be considered evaluable for response. These patients will have their response classified according to the definitions stated below.

Immune-Related Response Criteria (irRC)⁴³⁻⁴⁴: Novel criteria for the evaluation of antitumor responses with immunotherapeutic agents, as described in Wolchok *et al.* The patterns of response to immune therapy agents differ from those of cytotoxic therapy in several ways: There may be a transient worsening of disease before stabilization or regression, responses can take months to become apparent and may continue long after completion of the initial therapy, and prolonged periods of stable disease are common. For the purposes of this study, irRC will be used for evaluation of all **non-irradiated** index lesions and the unit of measure will be the sum of the products of the two largest perpendicular diameters (SPD) for all index lesions.

Response Evaluation Criteria in Solid Tumors (RECIST) Version 1.1⁴⁵: Method for the evaluation of antitumor responses to cytotoxic agents, as described by Eisenhauer *et al.* For the purposes of this study, RECIST 1.1 criteria will be used only for the evaluation of **irradiated** lesions and the unit of measure will be the single largest diameter.

Measurable lesions on initial imaging: Measurable malignant lesions on *initial* imaging are defined as those that can be accurately measured in at least one dimension as $\geq 10\text{ mm}$ ($\geq 1.0\text{ cm}$) with CT or PET/CT scan. Lymph nodes will be considered malignant (and thus measurable lesions) if their short axis is $\geq 15\text{ mm}$ ($\geq 1.5\text{ cm}$) by CT scan. All other lesions will be considered non-measurable disease. Bone lesions without a soft

tissue component, leptomeningeal disease, ascites, pleural/pericardial effusions, lymphangitis cutis/pneumonitis, inflammatory breast disease, and abdominal masses (not followed by CT or MRI), are considered non-measurable. Simple cysts are by definition non-malignant and non-measurable, but cystic metastases can be considered as measurable lesions, if they meet the size cutoff of measurability described above. Tumor lesions that are situated in a previously irradiated areas are not considered measurable.

Measureable lesions on follow-up imaging: Per irRC specifications, new measureable lesions on follow-up imaging will be defined as being $\geq 5 \times 5$ mm in size

Index lesions: All measurable lesions up to a maximum of 10 visceral lesions (≤ 5 per organ) and 5 cutaneous lesions, should be identified as index lesions and recorded and measured at baseline. Target lesions should be selected on the basis of their size (lesions with the longest diameter), be representative of all involved organs, and lend themselves to reproducible repeated measurements. It may be the case that, on occasion, the largest lesion does not lend itself to reproducible measurement in which circumstance the next largest lesion which can be measured reproducibly should be selected. It is preferable to exclude cystic metastases as index lesions if other non-cystic lesions are available. Prior to selecting index lesions a decision should be made on which lesion will receive an initial course of radiation therapy, as this lesion is not eligible to be considered as an index lesion to assess response to immune therapy. If any subsequent course(s) of radiation therapy are given to what was previously considered an index lesion, this lesion will no longer be considered an index lesion for subsequent systemic response assessment. The rationale for this is that including irradiated lesions in response assessment would bias the assessment of a systemic effect.

Tumor Burden: At the baseline tumor assessment, the sum of the products of the two largest perpendicular diameters (SPD) of all index lesions is calculated. At each subsequent tumor assessment, the SPD of the index lesions and of new, measurable lesions are added together to provide the total tumor burden: $\text{Tumor Burden} = \text{SPD}_{\text{index lesions}} + \text{SPD}_{\text{new, measurable lesions}}$.

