1.1. Primary Objective

To determine the best overall response rate (ORR) (complete and partial), as measured on follow-up CT or PET/CT imaging after initiation of radiation therapy.

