13.3. Methods for Analysis

Data will be summarized with respect to baseline characteristics and safety measurements using descriptive statistics (quantitative data) and contingency tables (qualitative data). The safety analysis will consist of AE summaries (frequency tables based on CTCAE grades) and laboratory abnormalities summary. For the primary endpoint, the response rate and its 95% confidence interval will be estimated with a binomial distribution. Univariate and multivariate logistic regression model will be used to assess the association between response and several radiotherapy variables (biologic effective dose,

number of lesions treated, sequence of radiation and immune therapy), tumor variables (irradiated tumor site, size, growth rate, histology, PD-L1 status, local response, extent of prior chemotherapy use, and biologic correlates), and patient variables (age, smoking status, and other factors associated with secondary immunodeficiency). A predictive nomogram for response will be developed based on the outcome of the multivariate analysis. In the data analysis on the secondary endpoints, the Kaplan-Meier method will be used to estimate overall survival and progression-free survival. Wilcoxon signed-rank test for paired data will be used to assess the change of quality of life scores between two visits. Since the lung cancer score (LCS) of the FACT-L focuses on lung cancer symptoms, this will be used for the primary QOL endpoint; however, the more general subscales of physical and functional well-being on the Trial Outcome Index (FACT-TOI) will also be collected. A difference of 3 LCS points will be considered clinically significant.¹²⁻¹³ Where applicable, comparison will be made to previous randomized trials assessing immune checkpoint inhibitors alone in a comparable patient population.

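### The denominator of the primary response rate is not settled: section 13.2 decides on 33 patients, section 11.1.2 classifies response only in a subset, and section 13.3 names no denominator

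*Combined protocol and SAP*

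**What the plan says.** Section 13.2 sets up a Simon two-stage minimax design. The first 18 patients are described as enrolled; then "an additional 15 patients will be treated for a total of 33 patients". The final rule is a count: "if 10 or fewer patients respond among 33 patients, the treatment will be concluded ineffective". Section 3.2 plans for about 33 enrolled and shows no allowance for losses.

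Section 11.1.2 defines who is evaluable for objective response: "Only those patients who have received at least one course of radiation therapy, and have had their disease re-evaluated by imaging", with that imaging at least 4 weeks after therapy begins. Only these patients have a response classified.

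Section 13.3 says that "the response rate and its 95% confidence interval will be estimated with a binomial distribution". It does not say of whom.

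Confirmation is required. Under 11.2.1, "best response assignment will depend on the achievement of both measurement and confirmation criteria", and the table in 11.2 defines irPR as at least a 50% "decrease in tumor burden compared with baseline in two observations at least 4 weeks apart". Complete response carries the same 4-week spacing.

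The start of the response period varies. The synopsis counts from the start of therapy. Section 1.1 has response "as measured on follow-up CT or PET/CT imaging after initiation of radiation therapy". Section 13.1 counts from after the first radiation course, and 11.2.1 from the start of treatment.

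Section 13.2 also limits the primary analysis to enrolment time-points (A) and (B), which the current section 3.1 does not define.

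**The concern.** Two sets of patients could serve as the denominator, and the plan does not choose between them. No section available for review says whether a patient who starts treatment but fails the 11.1.2 conditions counts as a non-responder, is left out or is replaced.

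Such patients are foreseeable. Section 3.3 allows radiation to be cancelled for illness, toxicity, decline or death. Section 11.1.1 allows scans up to 4 months apart, and section 4.1 admits patients with ECOG status 2.

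The omission is not neutral. The patients most likely to miss a qualifying scan are early failures. Leaving them out raises the estimate of the primary endpoint, and the choice could be made after the results are known.

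**Working it through.** **1. The plan's own figures.** Inputs from 13.2: n1 = 18, n = 33, final cut-off r = 10, p0 = 0.20, p1 = 0.40. With r1 as the largest stage-1 response count at which the trial stops:

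- P(early stop) = P(X1 ≤ r1), with X1 ~ Bin(18, p)
- P(declare active) = Σ over x > r1 of P(X1 = x) × P(X2 > 10 − x), with X2 ~ Bin(15, p)

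| r1 | Early stop at 0.20 | Alpha | Power |
|---|---|---|---|
| 4 | 0.716 | 0.0458 | 0.801 |
| 3 | 0.501 | 0.0497 | 0.825 |

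The stated early-termination probability of 0.72 is reproduced with 4 or fewer responses in 18. The written stage-1 rule stops at 15 or more progressions before any response. If everyone else is a responder, that is 3 or fewer responses, which gives 0.50. The rule and the probability do not agree. In addition, a patient without a scan is neither a progression nor a response under the written rule.

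**2. Direction of the effect.** A confirmed response needs two observations at least 4 weeks apart. If the first is made after treatment starts, the second falls at 4 weeks or later. A patient with no scan at 4 weeks or later therefore cannot be a confirmed responder, and excluding that patient removes a non-responder. The exception is a patient excluded only for not having had radiation, who could in principle respond to immune therapy. So the exclusion removes mostly, not only, non-responders.

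**3. Effect on the reported result.** Take 11 responses, the minimum that passes, with Clopper-Pearson limits:

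| Denominator | ORR | Exact 95% CI |
|---|---|---|
| 33 | 33.3% | 18.0 to 51.8 |
| 30 | 36.7% | 19.9 to 56.1 |
| 29 | 37.9% | 20.7 to 57.7 |
| 28 | 39.3% | 21.5 to 59.4 |

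**4. Expected shift.** If everyone lost is a non-responder, the expected ORR in the evaluable set is the true rate × 33/m, where m is the number evaluable:

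- True 20%: 0.20 × 33/30 = 22.0%; 0.20 × 33/28 = 23.6%
- True 40%: 0.40 × 33/30 = 44.0%; 0.40 × 33/28 = 47.1%

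The documents give no loss rate. The 3 to 5 patients lost here are an assumption.

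**5. Power if all 33 count.** Suppose the 20% and 40% rates do not already treat such patients as failures, and losses are unrelated to response. With a fraction f non-evaluable, the rates become 0.20(1 − f) and 0.40(1 − f), that is 0.19 and 0.38 at 5%, and 0.18 and 0.36 at 10%.

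| f | Power, r1 = 4 | Power, r1 = 3 |
|---|---|---|
| 5% | 0.733 | 0.759 |
| 10% | 0.653 | 0.680 |

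Alpha stays below 0.05 in all four cases.

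**The case against.** The strongest reply is that the sections are compatible. Section 13.2 fixes the test as a count out of 33, and 11.1.2 only says whose response is classified; an unclassified patient is simply not a responder. **For the final decision this stands.** If 11 responses are still required and nobody is replaced, the denominator of the estimate does not change the conclusion. It does not settle the estimate and interval in 13.3, which are the stated analysis of the primary endpoint.

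Three stronger readings are tempting, and the documents do not support them.

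- **The lower limit passing 20% at 29 evaluable changes the outcome.** It does not. No section tests the interval against 20%, and 11 of 33 already passes.
- **The type I error is inflated through replacement of non-evaluable patients.** The plan does not provide for replacement.
- **The comparison with earlier trials would favour the combination.** Section 13.3 says that "comparison will be made to previous randomized trials assessing immune checkpoint inhibitors alone" where applicable. That sentence follows the quality-of-life text and does not name the response rate. The denominators behind the earlier trials' rates are not given, so the direction of any bias in that comparison cannot be established.

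It is also fair to say that treating every lost patient as a non-responder is the extreme case, and that at a true 20% the shift is still only 2.0 to 3.6 points. The varying start of the response period is minor and has not been quantified. Part of the text between sections 3.6 and 4.1 was not available for review, so a rule there cannot be excluded.

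**Conclusion.** The concern holds for the reported primary ORR and its confidence interval, not for the final decision count. Sections 11.1.2, 13.2 and 13.3 leave two possible denominators, and the 11.1.2 set gives an upward-biased estimate because those it leaves out are mostly non-responders.

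On the same 11 responses, the ORR is 33.3% with all 33 counted and 36.7% to 39.3% with 30 to 28. These sizes rest on an assumed loss of 3 to 5 patients; the expected shifts also assume that all of them are non-responders.

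The same gap reaches stage 1, where a rule based on progressions has no place for a patient without a scan and does not match the stated 0.72. This should be corrected before analysis, but it does not undermine the design.

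**What to change.** In 13.2 and 13.3:

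- State that the decision counts, the primary ORR and its 95% CI use all eligible patients who start protocol treatment, without replacement. Define that start as the first immune-therapy cycle on study, which section 7.3 already uses for toxicity. Starting the count at radiation would bring back part of the exclusion.
- Count anyone without a confirmed irCR or irPR as a non-responder, including early death, no radiation or no qualifying scan.
- Report the 11.1.2 evaluable set as a labelled sensitivity analysis with its own denominator.
- Write the stage-1 rule as responses among the first 18, and reconcile the 15-or-more progressions with 0.72.
- Delete or update the (A)/(B)/(C) reference.

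Use the same start event in the synopsis and in sections 1.1 and 13.1.

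The cost is wording; no new data are needed. The reported ORR will be somewhat lower. If the 20% and 40% rates already count these patients as failures, the design's alpha and power are unchanged. If they do not, and losses are unrelated to response, power falls to about 0.73 at 5% and 0.65 at 10% non-evaluable with a stage-1 cut-off of 4, or 0.76 and 0.68 with 3. The sponsor should say which case applies and state the resulting power.
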